Economic analysis. Economic analysis is based on cost-effectiveness analysis (CEA), in which the alternative interventions are examined in the light of total cost per unit of health outcome. Incremental cost-effectiveness ratios will be calculated for the different frailty profiles, as the cost incurred to prevent one event, given that there was a significant reduction in the primary and secondary end-point, all-cause- and HF-related admissions, non-HF related admissions between groups. The time horizon will be equivalent to that observed during the period of the study (ie, no future projections are made). Moreover, a cost-utility analysis is programmed, calculating quality-adjusted life years (QALY) for each intervention group using the survival method and EuroQOL index as utility. To examine the impact of change in one or more variables on the results of the analysis, a sensitivity analysis where the cost of DMP and hospitalizations are changed of $\pm 10\%$ will be performed.

Study sample.

Based on previous studies (5,6), metanalyses (7-10) and national databases (3), the study sample is calculated to detect at least a 40% relative reduction at two years in the outcome of death and/or unplanned readmission for heart failure in the DMP, based on the assumption of a 60% event rate for the control group with a 0,05 alpha and 0,90 power. The planned sample size is at least 92 patients per group or, alternatively, the occurrence of 88 events.

Statistical Analysis.

In the primary Study, the two groups will be compared by the t test for normally distributed continuous variables and the chi square test for normal variables (with calculation of odds ratio [OR] and 95% confidence intervals [CI] where appropriate) and the Fisher exact test for variables with a prevalence <5%. Analyses are conducted according to an intention-to-treat approach. Kaplan-Meier survival curves are constructed to assess differences in deaths or readmissions between groups and compared using the log rank test. Data for all event-free patients are censored on study day 730. Event-free survivals are tested with the Cox proportional hazards method. Logistic regression analysis will be performed in order to identify factor potentially related to non-adherence to the program.

In the Secondary Study: Groups will be compared by the t test for normally distributed continuous variables (with Bonferroni correction as appropriate) and the chi square test and Fisher exact test for

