nominal variables. The predictive value of the Frailty Score and prognostic score index for the primary end-point will be compared by means of receiver operating curves (ROC). The intervention groups and frailty subgroups will be compared using multiple Cox proportional-hazards models, without and with adjustment for potentially confounding variables: age, sex, NYHA III-IV class, ischemic etiology, diabetes mellitus, atrial fibrillation, systolic blood pressure <100 mmHg, ejection fraction, anemia (hemoglobin ≤ 12 g/dl), serum sodium and creatinine levels, beta-blocker and ACE-inhibitor or Angiotensin receptor blockers treatment. NYHA III-IV class was not included in multivariable analysis of patients in stage 1 and stages 4-6. Differences in treatment effects according to frailty subgroups will be evaluated by tests of interaction and the statistical significance determined by a Wald chi-square test for interaction. Effects will be omitted from tables when a too small number of events were observed in the given analysis.

All analyses will be performed using SPSS for Windows (SPSS Inc. USA).

5. Variables collected

1. Baseline Demographic Characteristics and Multidimensional assessment.

Age (years) Gender (% Males) Education (years) Single/widowed/divorced (%) Living alone (%) Low financial income* No social/family support ≥2 IADL dependency** ≥1 BADL dependency** MMSE score Mean GDS 15 score

2. Baseline Clinical Characteristics

Body Mass Index (Kg/m²) Systolic Blood pressure (mmHG) Heart rate (b/min) Heart Failure etiology (Ischemic, Hypertensive, Dilated, Valvular, Other/multiple) Charlson comorbidity index § Comorbidities (Hypertension, Diabetes mellitus, Previous myocardial infarction, COPD NYHA class at discharge Mean LVEF (%) Serum Sodium (mmol/l) Creatinine clearance (ml/min) Hemoglobin (g/dl) Treatments at discharge: ACE-inhibitors, Angiotensin receptor blocker, Beta-blockers, Mean daily furosemide dose (mg), Spironolactone, Digoxin, Amiodarone, Nitrates, Anticoagulants

3. Outcomes.

Primary outcome variable: death from any cause and/or hospital admissions for HF. Secondary end-points: total and cardiovascular mortality, all-cause and HF-related admissions Costs of care

4. Quality of life and functional status.

Modified Frailty Score: Stage 1-6 EuroQol Index Mean ESCBs score

5. Quality of care.

Clinical status (NYHA)

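### The adjusted Cox models fitted within frailty strata carry 12 or 13 covariates on a share of 88 events, and the plan gives its better-behaved analyses no priority over them

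*Protocol*

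**What the plan says.** In protocol section 4, *Statistical Analysis* (Secondary Study), the comparison by frailty is set out as follows: "The intervention groups and frailty subgroups will be compared using multiple Cox proportional-hazards models, without and with adjustment for potentially confounding variables". Thirteen covariates are then named: age, sex, NYHA class, ischaemic aetiology, diabetes, atrial fibrillation, low systolic pressure, ejection fraction, anaemia, sodium, creatinine, beta-blocker, and ACE inhibitor or ARB.

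The next sentence reads "NYHA III-IV class was not included in multivariable analysis of patients in stage 1 and stages 4-6". A covariate can be left out for particular patients only if a model is fitted to those patients alone. Under *Measurments*, stage 1 is by definition NYHA II, so the covariate would be constant there. The adjusted model is therefore fitted stratum by stratum: stage 1, stages 4–6 and, by inference, stages 2–3.

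The same paragraph plans a Wald interaction test between treatment and frailty subgroup. It also says that results based on too few events will be left out of the tables, without saying how few is too few.

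Under *Study sample* the size is fixed: "The planned sample size is at least 92 patients per group or, alternatively, the occurrence of 88 events". No expected number of patients or events per frailty stage is given.

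**The concern.** A Cox model with 13 or 14 parameters needs far more events than a fraction of 88 can supply. With so few events per parameter, the reported standard error understates the real spread of the treatment estimate. Confidence intervals are then too narrow, tests reject too often, and a genuine effect is estimated too far from 1.

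The secondary aim is to use the frailty profile to decide who gains most from the programme and which model of care to choose. The *Economic analysis* paragraph adds cost-effectiveness ratios by frailty profile, conditional on a significant reduction in events. Adjusted hazard ratios by stratum are a natural source for both. An overfitted model could mark out a stratum as a responder by accident, or overstate a real benefit and the events prevented.

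**Working it through.** **Inputs from *Study sample* and *Statistical Analysis*.** Design: "with a 0,05 alpha and 0,90 power"; "based on the assumption of a 60% event rate for the control group"; "to detect at least a 40% relative reduction at two years". Follow-up: "Data for all event-free patients are censored on study day 730". Sidedness is not stated; two-sided reproduces the design.

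**The plan's own figure.**
- Event rates are 0.60 and 0.60 × (1 − 0.40) = 0.36. The implied hazard ratio is ln(0.64)/ln(0.40) = 0.487.
- Freedman: events = (1.960 + 1.282)² × [(1 + 0.487)/(1 − 0.487)]² = 88.3.
- Patients = 88.3/0.48 = 184, or 92 per group. Cross-check: 92 × (0.60 + 0.36) = 88.3 events.

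Both stated figures reproduce.

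**Events per parameter.** Assumption: an even split over three strata.
- 184/3 = 61 patients and 88/3 = 29.3 events per stratum.
- Stages 2–3: 13 covariates plus treatment, 29.3/14 = 2.1 events per parameter.
- Stage 1 and stages 4–6: 12 covariates plus treatment, 29.3/13 = 2.3.

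If there were truly no effect and both arms ran at 60%, there would be 184 × 0.60 = 110 events, or 37 per stratum. Runs with 29 to 37 events in 61 patients give the same 8–10% rejection.

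**Simulation of the adjusted stratum model** (Cox, treatment plus 12 or 13 covariates, 1,500–2,000 runs per main scenario, Monte Carlo error about 0.6 points). Covariate prevalences and effects are assumed, because the protocol gives none.

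| Patients / events in stratum | Rejection at HR 1, nominal 5% | Median adjusted HR when true HR is 0.487 |
|---|---|---|
| 90 / 43 | 7–8% | 0.44 |
| 61 / 29 | 8.1–9.4% (Wald), 8.9–10.2% (likelihood ratio) | 0.41–0.42 |
| 61 / 29, correlated covariates | 11.8% (Wald), 12.4% (likelihood ratio) | not run |
| 61 / 20 | 9–10% | 0.39–0.41 |
| 40 / 15 | 13–15% | 0.33–0.34 |

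- At 29 events and HR 0.487, the 95% interval covers the truth about 90% of the time.
- The mechanism shows even at 43 events with covariates that have no effect: the log hazard ratio has an empirical SD of 0.39 against an average reported standard error of 0.34. The adjusted median is then 0.443 and the unadjusted 0.485, so the shift comes from overfitting.
- At HR 1 the median adjusted hazard ratio stays near 1 (0.98–1.02).

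**Comparators.**
- Unadjusted stratum models: 4–5% rejection.
- Interaction Wald test fitted to all 184 patients and 88 events: 5.5% unadjusted, 6.6% with the 13 covariates.
- One joint model with treatment, stratum, interaction and four covariates has 1 + 2 + 2 + 4 = 9 parameters, or 88/9 = 9.8 events each. Stratum hazard ratios read from it reject in 4.6–5.5%. They are wrong by more than a factor of two in 9–13% of cases, against 21–33% for the separate models.

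**Chance of at least one false-positive stratum among three**, treating strata as independent: 1 − 0.95³ = 14% at nominal; 1 − 0.92³ = 22% to 1 − 0.90³ = 27% at 8–10%. These count both directions.

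**The case against.** A reader might infer that the programme's effect in each stratum comes only from the overfitted model, that it is always exaggerated, and that the secondary aim carries a 10% error rate. The protocol does not support that reading, for these reasons:

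- **Unadjusted models are planned too.** The same sentence says "without and with adjustment for potentially confounding variables", and the unadjusted stratum models hold their level.
- **Differences between strata have their own test.** The planned interaction test is near nominal if it is fitted to all patients.
- **A sparse-event rule exists.** A SAP that is not shown may give it a threshold.
- **The 29 events are not in the protocol.** The sample is a minimum and the stage distribution unknown. With 55 events in 92 patients, rejection is only 6–7%.
- **Exaggeration needs a true effect.** At HR 1 there is extra scatter without a systematic shift. Since about half of the false positives point to harm, a false responder appears in about 4–5% of strata.
- **Adjustment has some rationale.** Frailty subgroups are not randomised, and consent after allocation could unbalance the arms.

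All of this stands as a limit on the claim, but none of it repairs the adjusted stratum results. The protocol does not say which version prevails. The interaction test does not correct stratum hazard ratios or their intervals. A threshold-free rule can be applied after the results are seen. A large stratum also starves the others: if one takes 55 events, the other two share 88 − 55 = 33, or about 16 each. The case for adjusting is a case for a few strong prognostic variables, which 13 covariates on 29 events do not deliver.

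**Conclusion.** The point holds for the covariate-adjusted models within strata, which are one of two planned versions of a secondary analysis. The 8–10% rejection rate and the shift from 0.487 to about 0.41 rest on the even three-way split, on an inferred stages 2–3 stratum and on assumed covariate distributions. The direction does not depend on the split: every one tried left the test above its nominal level, and every one tried at HR 0.487 put the estimate too far from 1.

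The defect is in what the protocol states: a long fixed covariate list, refitted by stratum, with no precedence for the sounder analyses and no numerical floor on events. It should be corrected because the secondary aim is to guide selection of patients and model of care. It does not touch the primary comparison.

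**What to change.** Base the secondary aim on one Cox model in all randomised patients, with treatment, frailty stratum, treatment × stratum and a short set of baseline covariates named in advance whose effects are common to all strata. About four covariates is one reasonable choice; a penalised fit of the full list is another. Read the stratum hazard ratios, their intervals and the interaction test from that model. Report the already planned unadjusted stratum hazard ratios beside them, and drop the separate 12–13 covariate models.

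The cost is a change of analysis wording only. Fewer chance imbalances are adjusted for, and covariate effects are assumed equal across strata. When covariates are prognostic, the unadjusted hazard ratio lies closer to 1 than the adjusted one (0.535 at 43 events for a true conditional value of 0.487), so the two columns should be labelled as different quantities.

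The change removes distortion but not imprecision. With 29 events, power for a hazard ratio of 0.487 is 49% (Schoenfeld), and the standard error of the log hazard ratio is about 2/√29 = 0.37. Each interval then runs roughly a factor of exp(1.96 × 0.37) = 2.1 either side of the estimate.

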In both groups initial assessment will include history, physical examination and a multidimensional assessment (12) including education, marital status, financial income, social and emotional support, ability to perform basic (BADL) and instrumental (IADL) activities of daily living (13,14), cognitive status measure by means of the Folstein Mini Mental Status Examination, depressive symptoms measured by means of the Geriatric Depression scale, comorbidity will be quantified with the Charlson Comorbidity index (15), quality of life and self-perceived health, evaluated, respectively with the Minnesota Living with Heart Failure (MLwHF), a 5-item scale (from very good to very poor) and the EuroQOL (16). Disability is defined as an impairment in at least two IADL or at least one BADL.

An ad-hoc translated and validated local version of the European Self Care Behaviour scale (ESCB) will be administered in order to evaluate the baseline level of self-care (17). Frailty is measured by means of a modified frailty score (FS) (22), calculated combining five domains of functioning (age over 80, cognitive impairment defined as a MMSE score \leq 24, reduced mobility, urinary incontinence and physical impairment defined as a NYHA functional class III-IV) into six stages of increasing impairment. Stage 1 included patients <80 years, in II NYHA class and without impairments in mobility, continence, or cognitive function. Stages 2 to 6 included patients with the presence of one, two, three, four or all of the specific items, respectively. The risk profile of each patient will be also calculated by means of a prognostic score index .

Intervention

All patients will be discharged on optimized therapy and will receive before randomization a detailed summary and a standardized educational program focused on low-salt diet and drug therapy, self monitoring of blood pressure and symptoms, daily weight, smoke cessation, fluid intake and daily physical activity.

DMP Group. The program is based on a hybrid model, combining hospital clinic- and home-based care. In each of the two participating teams, the members will be a cardiologist experienced in geriatrics, two-to-four specialized nurses and the patient's primary care physician. According to ESC guidelines, the components of the program are: discharge planning, continuing education, therapy optimization, improved communication with health care providers, early attention to signs and symptoms and flexible diuretic regimen (11).

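### Cox models with 13 covariates fitted separately within frailty strata are overfitted: with about 29 events per stratum, the adjusted tests reject a true null about 9 to 10% of the time and exaggerate the treatment effect

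*Protocol*

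**What the plan says.** The secondary aim (protocol, Aims of the Study) is to use the frailty profile to find which patients gain most from the programme and to guide the choice of care model. The Secondary Study paragraph of Statistical Analysis sets out the analysis: "The intervention groups and frailty subgroups will be compared using multiple Cox proportional-hazards models, without and with adjustment for potentially confounding variables". Thirteen variables follow: age, sex, NYHA class, ischaemic cause, diabetes, atrial fibrillation, low systolic pressure, ejection fraction, anaemia, sodium, creatinine, beta-blocker use, and ACE inhibitor or receptor blocker use. The next sentence is an exception: "NYHA III-IV class was not included in multivariable analysis of patients in stage 1 and stages 4-6". Differences in treatment effect between frailty subgroups are to be judged by a Wald interaction test. A reporting rule closes the paragraph: "Effects will be omitted from tables when a too small number of events were observed in the given analysis".

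The frailty score (Measurments) counts five items: age over 80, MMSE of 24 or less, reduced mobility, urinary incontinence, and NYHA class III-IV. "Stage 1 included patients <80 years, in II NYHA class and without impairments in mobility, continence, or cognitive function". Stages 2 to 6 hold patients with one to five items.

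Under Study sample, "The planned sample size is at least 92 patients per group or, alternatively, the occurrence of 88 events". That figure is for the overall comparison. The protocol gives neither the number of frailty strata to be analysed nor their expected sizes or event counts.

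**The concern.** An exception that removes one covariate for patients in stage 1 and in stages 4-6 implies a separate adjusted model for each of those groups and, by inference, a third for stages 2-3. A trial sized for 88 events in total cannot support three models with 13 or 14 parameters each. With so few events per parameter, partial-likelihood estimates move away from the null and Wald standard errors are too small.

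The secondary aim is to say who benefits, and the Economic analysis section plans cost-effectiveness ratios by frailty profile. Overfitted stratum estimates can show a strong benefit in one frailty group by chance, with an interval too narrow to reveal it.

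Two smaller faults sit beside this one. The covariate set differs between strata for a reason that the staging rule only partly explains. Age and NYHA class are also both components of the score and adjustment covariates.

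**Working it through.** **1. The planned number of events.** Study sample asks to detect "at least a 40% relative reduction at two years in the outcome of death and/or unplanned readmission for heart failure", "based on the assumption of a 60% event rate for the control group with a 0,05 alpha and 0,90 power".
- Event rate under the programme: 0.60 × (1 − 0.40) = 0.36.
- Hazard ratio under proportional hazards: ln(0.64)/ln(0.40) = 0.487.
- Freedman's formula, two-sided alpha 0.05 (the protocol does not state sidedness): events = (1.960 + 1.282)² × [(1 + 0.487)/(1 − 0.487)]² = 88.3.
- Patients per group: 88.3/(0.60 + 0.36) = 92.0.

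Both planned figures reproduce, so 88 events is the right total to divide.

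**2. Parameters.** 13 covariates + treatment = 14. Where NYHA is dropped, 12 + 1 = 13.

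**3. Events per parameter, assuming three equal strata.** 184/3 ≈ 61 patients and 88/3 = 29.3 events. 29.3/14 = 2.1 per parameter; 29.3/13 = 2.3.

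**4. Simulation of one such stratum.** Two Cox simulations used different assumed covariates.
- *61 patients, about 30 events, 8 binary and 5 continuous covariates, log hazard ratio 0.15 each, 3,000 runs.* Type I error was 0.098 and 95% CI coverage 0.902. A true hazard ratio of 0.487 was estimated on average as 0.401. The SD of the log hazard ratio was 0.57 to 0.60, against 0.38 to 0.39 unadjusted.
- *61 patients, 29 events, 9 binary and 4 continuous covariates, coefficient 0 or 0.2 each.* Type I error was 0.094 to 0.102 with 14 parameters and 0.088 to 0.096 with 13. Unadjusted, it was 0.043 to 0.048. With a true hazard ratio of 0.487 the adjusted median was 0.40 to 0.42, and the mean log hazard ratio was 23 to 31% too large.

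**5. Other stratum sizes** (coefficient 0.2 per covariate):

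| Events / patients | Parameters | Adjusted type I error | Excess in mean log HR (true HR 0.487) |
|---|---|---|---|
| 15 / 46 | 13 | 0.127 | 56% |
| 22 / 46 | 14 | 0.112 | not run |
| 44 / 92 | 14 | 0.081 | 18% |
| 88 / 184 (whole trial) | 14 | 0.063 | 7% |

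**6. The interaction test.** If it is fitted on pooled data (3 strata, 2-df Wald test), the adjusted model has 13 + 1 + 2 + 2 = 18 parameters for 88 events. Type I error is 0.065 adjusted and 0.043 to 0.044 unadjusted.

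**7. NYHA class by stage.** In stage 1 every patient is NYHA II by definition, so NYHA must drop out. For the higher stages, count the item patterns that lack NYHA III-IV:
- Stage 4 (3 of 5 items): 10 patterns, of which 4 lack it.
- Stage 5 (4 of 5 items): 5 patterns, of which 1 lacks it.
- Stage 6 (all 5 items): 1 pattern, which includes it.

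NYHA is therefore constant by definition only in stage 6. These are counts of patterns, not of patients.

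**8. A pooled alternative.** One model in 183 patients, with categorical treatment-by-stratum terms and 3 covariates, 1,500 runs: type I error 0.051, coverage 0.949 to 0.954, and a true hazard ratio of 0.487 estimated on average as 0.484.

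**The case against.** The strongest reply is that the protocol already contains the safeguards. The models are planned both with and without adjustment, and the unadjusted ones hold their level. A claim that benefit differs by frailty should rest on the planned interaction test, which is close to nominal if pooled. Both points stand. A reader might infer that error rates are doubled throughout the frailty analysis, and the documents do not support that. What remains is that neither safeguard corrects the adjusted stratum hazard ratios and intervals, which the protocol also plans to produce.

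A second reply is that 29 events per stratum is not a figure in the protocol. That is correct. It follows from an assumption of three equal strata, and the third stratum is itself inferred. Unequal strata would make the small ones worse and the large ones milder. Even a stratum holding half of all events stays above 5%.

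A reader might also blame the differing covariate sets or the omission rule for the inflation. Neither causes it: 13 and 14 parameters perform almost alike. The omission rule depends on the number of events, not on the direction or size of the effect, so it does not amount to selecting favourable results. It lacks a threshold, which is minor and could be settled in a statistical analysis plan.

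Adjusting for age or NYHA does not remove frailty from a randomised treatment comparison within a stratum. The difficulty arises only when frailty groups are compared with each other. Finally, the NYHA exception is in the past tense, and a reader might infer that it was added after data were seen. The document cannot settle that.

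**Conclusion.** The concern holds for the covariate-adjusted models within frailty strata, and only for those. At about 29 events per stratum, the nominal 5% test runs at about 9 to 10%, nominal 95% intervals cover about 90%, and a hazard ratio of 0.487 is reported as about 0.40 to 0.42. Over strata of 15 to 44 events, type I error runs from about 13% down to 8%. These figures rest on the inferred within-stratum fitting, the assumed split of events, and assumed covariate prevalences and coefficients. The two sets of covariate assumptions at 29 to 30 events agree closely.

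Two separate, lesser faults stand without a measured size. Dropping NYHA is forced in stage 1 but unexplained in stages 4 and 5. Adjusting for age and NYHA when frailty groups are compared with each other removes part of what the score measures.

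The primary comparison is not affected. The point is worth correcting because the secondary aim depends on these estimates and the change is cheap.

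**What to change.** Delete the stratum-specific 13-covariate models and the NYHA exception. Replace them with one Cox model in all randomised patients containing:
- treatment;
- frailty category (the same strata, named in advance);
- categorical treatment-by-category terms, tested by the Wald interaction test already planned;
- at most 3 or 4 pre-named baseline covariates that are not components of the frailty score.

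With three categories this has 1 + 2 + 2 + 3 or 4 = 8 or 9 parameters, so 88 events give 88/9 = 9.8 to 88/8 = 11 events per parameter. Read the stratum hazard ratios and intervals from this model, keep the unadjusted analysis, and report every stratum with its event count and interval. This replaces the omission rule.

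A linear trend in the number of frailty items should be supplementary only. In simulation, when only the middle of three equal strata benefited (hazard ratios 1, 0.487, 1), the trend model put that stratum at about 0.80 with coverage of about 40% or less. Its 1-df test had 6.7% power, against 23% for the 2-df categorical test.

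The cost is a change of wording and less analysis work. The downsides are that fewer covariates are adjusted for and that covariate effects are assumed common across strata.

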Clinical management of older heart failure patients remains sub-optimal with subsequent high risk of mortality, morbility, poor quality of life and increasing costs, despite the availability of effective treatments (1-4). Available studies and systematic reviews suggest that elderly patients benefit from disease management programs (DMP) designed to improve quality of care and patient compliance and reduce hospital admissions with a beneficial cost-effectiveness ratio (5-10). However, results on other end-points and mortality are inconclusive. Furthermore, important questions are still open, including the most appropriate patient's selection process, the optimal follow-up intensity and duration and finally, whether such interventions are cost-effective during long-term follow-up and in different health care systems (7-10). Elderly patients include a heterogeneous population where the clinical status and subsequent risk profile result from a complex interaction between different domains (8): age-related cardiovascular changes, cardiovascular disease, comorbid conditions, age-related impairments and social issues (9). Multidimensional assessment (MA) is a validated diagnostic process to determine the medical, psychological, and functional capabilities and aimed at providing information for appropriate choice of care-plan and follow-up. One of the major goals of the MA is the identification of frailty. Frailty is a clinically recognized syndrome of loss of reserves (energy, physical ability, mobility, cognition, health) that gives rise to an increased vulnerability to stressors (e.g., concomitant acute illnesses, hospitalizations, medical procedures) and the risk of major events such as low-compliance, falls, disability, hospitalization and death, in subjects with or without HF. Although the focus of MA is the frail or disabled elderly, this approach was rarely used in previous studies on HF and never used to evaluate model effectiveness.

3. Aims of the Study

The primary aim of this study is to determine the long-term efficacy of an interdisciplinary DMP involving cardiologist, primary care physician and nurse, combining pre- and post-discharge care and following patients for two years. The secondary aim is to evaluate if the frailty profile should be useful to identify which HF elderly patient may benefit mostly from a DMP and select the appropriate model of care.

4. Study plan, Patients and methods

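### Leaving effects out of the tables when events are too few, with no cut-off and no duty to show counts, makes reporting on the frailty aim depend on the outcome

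*Protocol*

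**What the plan says.** The sentence closes the Secondary Study part of the Statistical Analysis paragraph in the protocol (section 4): "Effects will be omitted from tables when a too small number of events were observed in the given analysis". Nothing around it defines too small, says whether the count is per stratum or per arm, or requires patient and event numbers for an omitted result.

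The analyses it governs serve the aim in section 3: "The secondary aim is to evaluate if the frailty profile should be useful to identify which HF elderly patient may benefit mostly from a DMP". Frailty is graded "into six stages of increasing impairment" (section 4, baseline measurements). The remark that "NYHA III-IV class was not included in multivariable analysis of patients in stage 1 and stages 4-6" suggests that the stages may be pooled into 1, 2-3 and 4-6, though the protocol does not say so outright. Stage sizes are not given.

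The sentences just before the rule set out the formal comparison: "Differences in treatment effects according to frailty subgroups will be evaluated by tests of interaction", with significance from a Wald chi-square test.

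**The concern.** The rule is triggered by the result. In a given stratum the number of events depends on the number of patients, their baseline risk and the effect of the programme. The third is what the secondary aim is meant to estimate. Between two strata of equal size and baseline risk, the one in which the programme works better is therefore more likely to go unreported. With no cut-off fixed, the decision is also made by someone who already knows the events.

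The planned size is 92 per group, to be spread over up to six stages and several endpoints, so sparse cells are foreseeable. If a frailty profile is missing from the tables, a reader may take the profiles shown as the only ones with evidence, and cannot set the interaction test beside the strata that entered it.

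**Working it through.** **1. The planning effect.** The protocol's Study sample paragraph plans for "at least a 40% relative reduction at two years in the outcome of death and/or unplanned readmission for heart failure", "based on the assumption of a 60% event rate for the control group with a 0,05 alpha and 0,90 power". Control risk is 0.60 and DMP risk 0.60 × (1 − 0.40) = 0.36.

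- Hazard ratio = ln(1 − 0.36) / ln(1 − 0.60) = 0.487.
- Freedman events, two-sided alpha 0.05 (sidedness assumed) and power 0.90: (1.960 + 1.282)² × [(1 + 0.487)/(1 − 0.487)]² = 88.3.
- Patients per group = 88.3 / (0.60 + 0.36) = 91.99, that is 92.

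This reproduces the protocol's 92 per group and 88 events, so 0.487 is the effect that the plan assumes.

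**2. Assumptions for the rule.** The protocol gives no stratum size, stratum risk or cut-off. Assumed:

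- stratum size of 15 per arm (92/6, six equal stages) or 31 per arm (92/3, three equal groups);
- control risk of 60% (the planned rate), 40% or 30%;
- omission if total events are below 10, or if either arm has fewer than 5.

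**3. Probability of omission, total-event cut-off.** Events in the two arms are independent binomials. DMP risk = 1 − (1 − p)^HR, so p = 0.40 gives 0.220 and p = 0.60 gives 0.36. P(omit) = P(X + Y < 10), by exact convolution.

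| Per arm | Control risk | No effect | HR 0.487 |
|---|---|---|---|
| 15 | 40% | 17.6% | 54.1% |
| 15 | 60% | 0.1% | 3.1% |
| 20 | 30% | 19.6% | 56.0% |
| 30 | 30% | 0.6% | 8.7% |
| 31 | 40% | 0.0% | 0.2% |
| 31 | 60% | 0.0% | 0.0% |

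The cut-off matters as much. In the first row, a cut-off of 8 gives 4.4% and 23.8%, and a cut-off of 5 gives 0.2% and 2.1%.

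**4. Size and baseline risk compared with benefit.** With 15 per arm, 30% control risk and no benefit, the stratum is omitted 58.9% of the time. An equally small stratum at 60% risk with the planned benefit is omitted 3.1% of the time. Benefit raises omission at fixed size and risk, but it need not be the main driver.

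**5. Per-arm cut-off.** The text also permits this reading. With omission if either arm has fewer than 5 events, at relative risks of 1.0 / 0.6 / 0.4:

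- 15 per arm, 60% risk: 1.9% / 32.9% / 72.2%
- 31 per arm, 60% risk: 0.0% / 0.4% / 10.3%
- 31 per arm, 30% risk: 4.7% / 33.7% / 69.5%

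**6. Are the effects that remain biased?** Mean log odds ratio (0.5 added to each cell), all trials against trials in which the effect is shown, true relative risk 0.6:

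| Rule | Per arm, control risk | All | Shown |
|---|---|---|---|
| Total < 10 | 15, 60% | −0.983 | −0.983 |
| Total < 10 | 15, 30% | −0.667 | −0.671 |
| Either arm < 5 | 15, 60% | −0.983 | −0.705 |
| Either arm < 5 | 31, 30% | −0.670 | −0.437 |

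A total-event cut-off leaves the displayed relative effects essentially unchanged. A per-arm cut-off shrinks them towards no effect.

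**The case against.** The best defence is that the sentence is ordinary prudence. The frailty Cox models may adjust for 13 listed covariates, and with few events such models give unstable or non-convergent hazard ratios. The sentence speaks of effects, so it can be read as suppressing those estimates without withholding counts, and table layout is commonly left to an analysis plan. At the planned 60% control rate with a total-event cut-off, omission is rare.

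Much of this stands. Suppressing a hazard ratio that cannot be estimated is reasonable, and the size of the problem rests on assumptions that the protocol neither confirms nor excludes. It does not rescue the sentence, however. The protocol has itself fixed a reporting rule, left its trigger undefined and required nothing in place of what is omitted. A numerical threshold would remove the discretion but not the dependence on outcome.

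Two stronger readings are tempting. A reader might infer that the rule biases the answer on who benefits. The documents do not support that: the rule is about tables, nothing removes sparse strata from the models or from the Wald interaction test, and displayed relative effects are distorted only under a per-arm count, which the protocol permits but does not state. A reader might also infer that a stratum vanishes chiefly when the programme works. Step 4 shows that small size or low risk can do it with no benefit.

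**Conclusion.** The concern holds as one of selective, outcome-dependent reporting on the secondary aim. For a stratum of given size and baseline risk, benefit raises the chance that its effect is not shown. The size ranges from negligible (31 per arm at the planned 60% risk, total-event cut-off) to about a threefold rise (17.6% to 54.1% with 15 per arm, 40% risk and a cut-off of 10). Under a per-arm cut-off of 5, with 15 per arm and 60% risk, the displayed log odds ratio is attenuated from −0.983 to −0.705.

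All of these rest on assumed stratum sizes and cut-offs, and those away from 60% also on assumed control risks. Bias in the interaction test is not shown, and the primary comparison and the planned 92 per group or 88 events are untouched. Severity is minor to moderate.

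**What to change.** Delete the sentence. In its place, state that every planned frailty stratum and endpoint will be tabulated with patients, events in each arm and the two-year risk difference with an exact or score 95% confidence interval. Where the Cox model cannot be fitted, enter only the hazard ratio as not estimable and keep the rest of the row.

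The cost is one sentence in the protocol and a few table rows. Some printed intervals will be wide, which is a fair picture of the information in those strata. Sample size, models and the interaction test do not change.
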